4.7.3 Perinatal Outcomes

For the purpose of assessing possible effects of antenatal care on perinatal outcome, it is important to distinguish between intrauterine events (with fetal death as the extreme example) and events occurring after the birth of a living child.

Adverse intrauterine conditions may lead to permanent disability or impairment of mental or physical functions. Chronic malnutrition may lead to growth retardation and fetal death. Some fetal conditions can be detected and risk assessed through antenatal surveillance (smoking, syphilis, fetal growth retardation). Some risk factors can be partially removed through changes in behavior (smoking), treatment (syphilis) or by induction of birth to save a severely growth-retarded fetus (elective versus emergency cesarean section).

Death or disease during the first week of life is likely to result from intrauterine conditions which may occur either before or during birth, but also from events after birth, particularly among preterm and LBW infants. When perinatal mortality diminishes, as it has in industrialized countries, the relative share of stillbirth is higher (about 50% of perinatal mortality). The primary outcome of the study in relation to fetal conditions will be the **rate of low birth weight (< 2500 g)**. It is considered very unlikely that ANC will influence perinatal mortality without changing the rate of LBW. Because of the difficulties in obtaining reliable gestational age for this large population under different clinical care, it is not possible to differentiate between preterm delivery and SGA as is recommended in the literature.

4.7.4 Process variables

The definition of process variables will not include a description of the antenatal care system, such as number of antenatal care visits and content of each visit, because this is the description of the implementation of the treatment or intervention, and not a process variable. The intervention will be described and its compliance documented as is done in clinical trials (urine or serum level of a drug or number of tablets taken).

Table 6 enumerates the outcome variables of the study:

4.8 Sample Size

4.8.1 Background

Sample size estimates depend on a number of practical and statistical considerations, some of which can only be surmised and several of which are somewhat arbitrary. Factors that influence sample size are:

1. major outcome variables of interest;
2. pre-intervention level of the major end-points, and the variability of the endpoints in the absence of intervention;
3. effect of intervention on the endpoints selected for study;
4. the chance of claiming that an effect intervention has occurred, when in fact, no effect was present: the alpha level corresponding to the statistical test of significance;
5. the chance of failing to detect an effect of intervention, when in fact, an effect was present: $\beta = 1 - \text{power of the test of significance}$;
6. participation rates of both individuals and entire clusters;

Table 6 : Outcomes of the ANC Randomized Controlled Trial

A. PRIMARY OUTCOMES	Question number in Data Collection Form(s)	Rate
Rate of maternal morbidity indicator index ⁽⁺⁾	See individual items	> 10%
Rate of LBW (<2500g)	50	> 10%
B. SECONDARY OUTCOMES		
Incidence of proteinuric ^(*) -pre-eclampsia or eclampsia	27	
Prevalence of post partum anemia (hemoglobin <90g/l) ^(**)	38	
Incidence of severe urinary tract infection/pyelonephritis (requiring antibiotic treatment ^(***) or hospitalization)	28 and hospital admission	
Rate of treated syphilis and any other STDs	31	
Rate of post-partum positive syphilis test ^(***) (among women without treatment during pregnancy)	39	
Rate of incomplete tetanus immunization	21	
Rate of post partum hospital stay ≥ 7 days for maternal complications	41-42	
Rate of IUGR ^(#)		
Rate of preterm delivery (<37 weeks)	52	
Rate of spontaneous & PROM pre-term delivery : <35weeks : 35-36 weeks	36	
Rate of medically indicated pre-term delivery : <35 weeks : 35-36 weeks	36-37	
Rate of breech presentation at birth	48	
Rate of very LBW (<1500 g)	50	
Rate of Apgar score <5 at 5'	53	
Rate of I.C.U. stay > 2 days	55 (c)	
Rate of fetal death	49	
Rate of pre-discharge neonatal death	56	

* Proteinuria of 2.0 g or more in 24h or 2+ or more on qualitative examination (dipstick)

** Requires postpartum blood samples

*** Excluding the antibiotics given to treat asymptomatic bacteriuria

+ Maternal morbidity indicator index: the presence of at least one of the following:

proteinuric-preeclampsia or eclampsia (during pregnancy or within 24 h of delivery; post-partum anemia (<90 g/l); severe urinary tract infection/pyelonephritis (requiring antibiotic treatment or hospitalization)

If LNMP not available, use the best "obstetric" estimation; below 10th percentile of international standard

OUTCOMES OF THE ANC RANDOMIZED CONTROLLED TRIAL
(contd.)

C. PROCESS OUTCOMES	Question number in Data Collection Form(s)	Rates
Rate of antenatal hospital admission - total by cause	Hospital admission form	
Rate of elective and emergency cesarean section associated with pregnancy complications (****)	36-46-47 of Summary form	
Days of hospital admission during pregnancy (median)	Hospital admission form	
D. COST OF ANC	Mean (SD) in US\$	
To the health service		
To the patient		
E. SATISFACTION AND PERCEIVED QUALITY OF CARE (only in random sample)		
By the health workers		
By the patient		

**** Excluding intrapartum cesarean section for fetal distress or cephalopelvic disproportion

7. duration of study;
8. loss to follow-up;
9. randomization by cluster;
10. use of randomized pairs or randomized blocks to increase the precision of comparisons;
11. study areas (countries; sites within country; clinics or hospitals within areas).

Changing the specification of any one of the above factors can have a major effect on the estimate of the sample size. Some of these factors have specific relevance in reference to the present protocol.

The major endpoint

Any one of the many endpoints of interest itemized in the protocol can be used to estimate the required size of this study, with the sample size varying by the endpoint chosen. Among these endpoints, there are two primary outcomes of major public health importance which the new programme must demonstrate will not increase: namely, the maternal morbidity index and low birth weight. Thus, the average minimum rate obtained for individual rates from areas to be enrolled in the study (about 10%) will be used to plan the size of the proposed investigation.

Baseline values

It is reasonable to expect to identify areas where this rate (10%) ranges from a low of about 7 per 1000 live births to a high of about 13 per 1000 live births. Since the areas of study will not be homogeneous in their LBW, the estimate of sample size has to take this into account. The sample size analysis also has to account for the use of cluster randomization, rather than individual patient randomization (see 4.2.2., Unit of Randomization).

Effect of Intervention

The new system of antenatal care is expected to have no major adverse effect on perinatal mortality. The design of study to reliably confirm such an hypothesis, if indeed it is true, would be prohibitive in terms of the required number of patients and study areas, unless, of course, the new system of care has a substantial beneficial effect, which is not expected either. Thus, before attempting to confirm an hypothesis of "minimal" or "negligible" effect, it seems sensible first to plan a study designed to determine whether such a supposition is even plausible.

Randomization

The unit of randomization will be a **cluster**, which will consist of a clinic or a group of small clinics within a geographic or administrative area (see 4.2.2, Randomization by Unit).

A gain in design efficiency is possible in principle by using randomized pairs with a corresponding pair-matched analysis. The gain in efficiency from pairing depends on how close the matching can be done relative to the variability in rates across the study areas. Although this design is attractive, there are several associated drawbacks that make it a less acceptable option (Martin et al., 1993). The most important limitation is the inability to consistently estimate the within-cluster intraclass correlation coefficient with respect to the response variable of interest. A detailed description of the limitation and the implication for data analysis can be found in Donner and Klor (1994).

Study areas

The particular areas of study, the countries, clinics and hospitals should have an infrastructure that can support an intervention trial, including sufficient numbers of

patients for follow-up. The areas chosen for study span a range of primary outcome rates, so that results of the investigation can apply across a spectrum of settings.

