Subject number list forms were used to record names and some information of every subject recruited into the study. Classifying forms were used to classify women only in the intervention hospitals into low and high risk groups. Low risk women received new basic antenatal care scheme. High risk women were managed according to the recommended treatment in that hospital or referred to a higher level of care. Antenatal hospital admission forms were completed for women admitted to the hospital for various conditions before delivery. Summary forms were completed for all women recruited into the study regardless of their pregnancy outcomes.

Principal investigators or coinvestigators or field coordinators visited these 12 hospitals fortnightly during the first 3 months and once a month for the rest of the 12 month recruitment and 6 month follow up period. This was to ensure a good quality recruitment, follow up and data collection procedure.

Responsible persons in each hospital were requested to send all forms (subject number list, classifying forms (in intervention hospitals), antenatal hospital admission and summary forms) monthly to the provincial health office where the field coordinators checked the actual number of forms received with the number indicated in the batch cover form. All forms were transferred from the provincial health office to the data coordinating unit at the Faculty of Medicine, Khon Kaen University. Data were doubly entered using the SPSS/DMS2 program provided by the Special Programme of Research, Development and Research Training in Human Reproduction, The World Health Organization, Geneva, Switzerland. Data were checked by various checking mechanisms. Query sheets were produced and sent to respective hospitals by facsimile. Update of the data was performed when response was obtained from hospitals. Data were transferred monthly to the central coordinating unit in Geneva via electronic mail. Summary forms for maternal deaths, fetal deaths and eclampsia cases had to be faxed to the coordinating unit in Khon Kaen University as soon as possible. These forms were then transferred to the central coordinating unit in Geneva also by fax. Number of these adverse outcomes by arms of the trial were reported periodically to the data safety monitoring committee only.

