d) Pre-eclampsia admitted to hospital
e) Eclampsia

29. Urinary tract infection

- 1 = No
2 = Yes, no treatment
3 = Yes, with antibiotic treatment
4 = Yes, with hospital admission

30. Vaginal bleeding during pregnancy

- 1 = No 2 = Yes

- a) First trimester
b) Second trimester
c) Third trimester

31. Lowest haemoglobin value during pregnancy g/l

Grid for lowest haemoglobin value

32. Was the mother treated for any of the following conditions during pregnancy?

- 1 = No 2 = Yes

- a) Trichomoniasis, moniliasis or any other abnormal discharge
b) Syphilis
c) Any other sexually transmitted diseases

33. Was external version for breech or malpresentation attempted?

- 1 = No, cephalic presentation
2 = Breech or malpresentation, no version attempted
3 = Version attempted

34. Prelabour rupture of membranes

- 1 = No 2 = Yes

164

Subject number

Grid for subject number

LABOUR AND DELIVERY

35. At admission in labour, did the mother have any of the following conditions?
1 = No
2 = Yes, noted during antenatal period
3 = Yes, first noted at admission

- a) Pregnancy induced hypertension
b) Pre-eclampsia
c) Severe anaemia (< 70 g/l)
d) Chronic hypertension
e) Uterine height low for gestational age
f) Malpresentation or breech
g) Multiple gestation
h) Pyelonephritis or urinary infection
i) Vaginal bleeding
j) Diabetes mellitus
k) Cardiac disease
l) Chronic respiratory conditions
m) Renal disease
n) Pelvic mass
o) Isoimmunization Rh(-)
p) Other

36. Fetal heart rate present at admission in labour
1 = No 2 = Yes

37. Onset of labour
1 = Spontaneous
2 = Induction (Complete Question 38)
3 = Elective caesarean section

38. Indications for induction of labour
1 = No 2 = Yes

- a) Prelabour rupture of membranes
b) Post-term
c) Intrauterine growth retardation
d) Chronic fetal distress
e) Pre-eclampsia
f) Maternal medical complications
g) Pregnancy complications
h) Isoimmunization Rh(-)

POSTPARTUM INFORMATION

39. Lowest haemoglobin value g/l

Grid for haemoglobin value

40. Syphilis test
1 = Negative 2 = Positive

Grid for syphilis test

41. a) Maternal death
1 = No 2 = Yes
b) If Yes, cause of death

Grid for maternal death

ICD-10 code

42. Date of mother's discharge from hospital or death

Grid for date of discharge

NEONATAL OUTCOME

43. Date of delivery or abortion

Grid for date of delivery

44. Time of delivery

Grid for time of delivery

45. Total number of fetuses

Grid for total number of fetuses

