If more than 1 fetus, please fill additional Summary form, completing Identification and Neonatal Outcome (Q43 - Q60)

46. Birth order (if multiple delivery)

Grid for birth order

47. Mode of delivery

- 1 = Spontaneous
2 = Elective caesarean section (Complete Question 48)
3 = Intrapartum caesarean section (Complete Question 48)
4 = Vacuum
5 = Forceps
6 = Assisted breech or breech extraction
7 = Internal version and extraction

165

Subject number

Grid for subject number

48. If caesarean section, indications

1 = No 2 = Yes

- a) Fetal distress
b) Failure to progress
c) Breech or other malpresentation
d) Maternal medical complications
e) Pregnancy complications
f) Previous caesarean section
g) Multiple pregnancy
h) Cephalopelvic disproportion
i) Intrauterine growth retardation
j) Other

Vertical grid for caesarean section indications

49. Fetal presentation at delivery

1 = Cephalic
2 = Breech
3 = Other

Grid for fetal presentation

50. Status at birth:

1 = Live birth
2 = Fresh stillbirth
3 = Macerated stillbirth

Grid for status at birth

51. Birthweight

g Grid for birthweight

52. Infant sex

1 = Male
2 = Female

Grid for infant sex

53. Gestational age at birth or abortion (best obstetric estimate) Completed weeks

Grid for gestational age

54. Apgar score

- a) at 1 minute
b) at 5 minutes

Grid for Apgar scores

55. a) Any congenital malformations?

1 = No 2 = Yes

b) If Yes, specify ICD-10 code

56. a) Admission of the newborn to Intensive Care Unit or any special care unit

1 = No 2 = Yes

b) If Yes, specify the principal reason

ICD-10 code

c) If Yes, specify the number of days in Intensive Care Unit or any special care unit

Grid for number of days

57. a) Newborn status at discharge

1 = Alive
2 = Dead
3 = Referred to another hospital or unit

Grid for newborn status

b) If dead, cause of death

ICD-10 code

58. a) If referred to another hospital or unit, status at 7th day of life

1 = Alive
2 = Dead

Grid for status at 7th day

b) If dead, cause of death

ICD-10 code

59. Date of newborn's discharge from hospital or death

Grid for date (day, month, year)

60. If dead, time of death

Grid for time of death (hour, minute)

REMARKS

Large text area for remarks

Hospital code

Grid for hospital code

Recorder number

Grid for recorder number

Signature

Date

BASIC ANTENATAL CARE CHECKLIST

CHECK THE ACTIVITIES CARRIED OUT WHERE APPROPRIATE (UNSHADED BOXES)

Use the closest gestational age at the time of visit

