Rate of treated syphilis and any other STDs			
Rate of post-partum positive syphilis test ^(***) (among women without treatment during pregnancy)			
Rate of incomplete tetanus immunization			
Rate of post partum hospital stay ≥7 days for maternal complications			
Rate of IUGR ^(#)			
Rate of preterm delivery (<37 weeks)			
Rate of spontaneous & PROM pre-term delivery : <35weeks : 35-36 weeks			
Rate of medically indicated pre-term delivery : <35 weeks : 35-36 weeks			
Rate of breech presentation at birth			
Rate of very LBW (<1500 g)			
Rate of Apgar score <5 at 5'			
Rate of I.C.U. stay > 2 days			
Rate of fetal death			
Rate of pre-discharge neonatal death			

* Proteinuria of 2.0 g or more in 24h or 2+ or more on qualitative examination (dipstick)

** Requires postpartum blood samples

*** Excluding the antibiotics given to treat asymptomatic bacteriuria

- Maternal morbidity indicator index: the presence of at least one of the following:

proteinuric-preeclampsia, eclampsia, severe hypertension (≥ 160/110 mmHg)(during pregnancy or within 24 h of delivery; post-partum anemia (<90 g/l); severe urinary tract infection/pyelonephritis (requiring antibiotic treatment or hospitalization)

If LNMP not available, use the best "obstetric" estimation; below 10th percentile of international standard

Table VII: PERINATAL DEATHS BY "INTENTION TO TREAT"
AND BY ANTENATAL CARE PROGRAMME

PERINATAL DEATH BY AGE AT DEATH	CLUSTERS		Relative risk (95% CI)
	Intervention	Control	
	(N=	(N=)	
Fetal deaths:			
Fresh stillbirth			
Macerated stillbirth			
Neonatal deaths:			
0 - 6 days			
7 - 27 days			

Table VIII: MATERNAL DEATHS BY "INTENTION TO TREAT"
AND BY ANTENATAL CARE PROGRAMME

MATERNAL DEATHS BY TIME OF DEATH	CLUSTERS		Relative risk (95% CI)
	Intervention	Control	
	(N=)	(N=)	
During pregnancy			
During labour and delivery			
Post partum			

Table IX: ADVERSE PREGNANCY OUTCOMES BY "INTENTION TO TREAT"
AND BY ANTENATAL CARE PROGRAMME

	CLUSTERS		Relative risk (95% CI)
	Intervention	Control	
	(N=)	(N=)	
Undiagnosed multiple pregnancies (%)			
Undiagnosed grossly IUGR (%)			
Severe anemia (<90g/l) at birth (%)			
Undiagnosed malpresentations at start of labour (%)			
Eclampsia (%)			
Untreated malaria (%)			
Untreated syphilis (%)			
Untreated other infections (i.e. tuberculosis) (%)			

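### The secondary outcome of a postpartum stay of 7 days or more for maternal complications cannot be scored as defined, because no form records why the mother stayed

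*Protocol*

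**What the plan says.** Table 6 (Outcomes of the ANC Randomized Controlled Trial, printed within section 4.8.1) lists the secondary outcome "Rate of post partum hospital stay ≥ 7 days for maternal complications" and gives its source as items 41-42 of the data collection form. Table VI in Appendix III carries the same row, "Rate of post partum hospital stay ≥7 days for maternal complications", for the comparison by intention to treat.

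In Appendix I, the postpartum block of the Summary form has four items: "39. Lowest haemoglobin value g/l", a syphilis test (40), "41. a) Maternal death" with its cause, and "42. Date of mother's discharge from hospital or death". The next block begins with "43. Date of delivery or abortion". For a newborn admitted to intensive or special care, the same form asks "b) If Yes, specify the principal reason" (56b) and the number of days (56c).

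The section on implementation in Khon Kaen says of the other clinical form: "Antenatal hospital admission forms were completed for women admitted to the hospital for various conditions before delivery". Section 4.9.1 has the hospital data clerk complete the summary and hospital admission forms within 24 hours of delivery.

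**The concern.** The outcome has two conditions: the stay lasts at least 7 days, and maternal complications are the reason. The form supplies the first but has no item for the second. Mothers who stay because the baby is preterm or in special care, or for social or organisational reasons, cannot be told apart from those who stay because they are ill.

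What is at stake is the meaning of one row in the secondary outcome table. A rate labelled as maternal morbidity would partly follow newborn stay, and so preterm birth and low birth weight. Low birth weight is already a primary outcome and preterm delivery another secondary one. The row also matters more than its place in the list suggests. Apart from anaemia, and hypertension within 24 hours of delivery, it is the Table 6 outcome best placed to register severe illness after birth. The form has no item for postpartum haemorrhage or sepsis, yet section 5.2.6 names both among the causes of the Thai maternal deaths.

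**Working it through.** **1. Which items does Table 6 mean?** The Table 6 item numbers were compared with the printed Summary form. All 17 that were matched are one too low. Examples:

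- low birth weight: Table 6 gives 50, the form has 51
- pre-eclampsia or eclampsia: 27, form 28
- urinary tract infection: 28, form 29
- postpartum anaemia: 38, form 39
- preterm delivery: 52, form 53
- Apgar score: 53, form 54

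The reference 41-42 therefore has two readings:

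- Literal: item 41 (maternal death and cause) and item 42 (date of discharge or death). There is no delivery date, so no length of stay.
- Shifted by one: item 42 and item 43 (date of delivery or abortion). Length of stay = item 42 minus item 43.

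The second is plainly intended. Neither contains a reason for the stay.

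**2. Is the reason recorded elsewhere?**

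- Postpartum block (39-42): haemoglobin, syphilis test, death with cause, one date. Only a woman who dies has a cause recorded.
- Items 28, 29, 35 and 48: hypertensive disorders, urinary infection, conditions at admission in labour, caesarean indications. These describe pregnancy, the start of labour and the operation, not why the woman was still in hospital a week later.
- Hospital admission form: described as covering admissions before delivery.
- Items 56a to 56c: admission, reason and days for the newborn only.

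The computable variable is (item 42 − item 43) ≥ 7 days, any reason. The defined variable also needs an attribution that is not collected.

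**3. Timing.** Within 24 hours of delivery, item 42 minus item 43 is at most about one day for any mother already discharged. For a mother still in hospital, item 42 does not yet exist. A stay of 7 days cannot be known then, so section 4.9.1 and item 42 need reconciling.

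**4. Ceiling on the death question.** Item 42 is a single field for discharge and death. By plain subtraction, a death on day 3 gives 3 days, which is below 7. The Thai data bound the effect:

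- Deaths: 8 (section 5.2.6). Summary forms: 6583 (Table 17).
- The Discussion's own figure is 122 per 100,000. Check: 8/6583 = 121.5, and 8/6560 = 122.0, where 6560 = 6583 − 23 not pregnant. Both round to 122, so it is reproduced.
- If all 8 deaths were postpartum, in hospital and before day 7, the rate would change by 8/6583 = 0.12 percentage points.
- If all were also in one arm: 8/3379 = 0.24 points (intervention) or 8/3204 = 0.25 points (control).

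These are upper limits, because the timing of the deaths is not in the text at hand.

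**The case against.** The best reply is that much can be rescued. Length of stay is computable, so the outcome is not lost altogether. Items 28, 29, 35, 39 and 48 describe maternal conditions, and 56a to 56c allow a check on newborn-driven stays. A manual of operation was given to each hospital and may hold coding instructions. The forms also carry clinic and hospital record numbers, so notes could be consulted. And this is one secondary outcome of 17.

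Most of this stands, and it limits the point to the attribution. It does not supply the attribution. The listed items do not give the reason for the mother's stay, the protocol gives no rule for inferring it from them, and it sets up no retrieval from notes for this outcome. An analysis plan cannot derive a cause that the forms did not collect.

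A reader might go further and infer that the plan counts a mother who dies in the first week as a good result. The documents do not say so. That follows only from subtracting dates while ignoring item 41a, printed just above the date. Table VIII reports maternal deaths by arm with a postpartum row, and such a derivation rule is commonly left to an analysis plan.

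A reader might also try to size the newborn-driven stays by applying some share to the 8.4% preterm rate. Nothing in the documents says how many mothers stay in with their babies, so any such figure would be a guess.

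**Conclusion.** The point holds for the attribution. As defined in Tables 6 and VI, the outcome has no source item for its qualifying condition. Only a stay of 7 days or more for any reason can be derived. The wrong item numbers and the 24-hour completion rule are further defects affecting the same row.

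The amount of misclassification cannot be stated, because the documents report no rate for this outcome and no reasons for stay. Nothing shows that it would differ between arms. The handling of early deaths is a minor matter of at most 0.12 points overall in the Thai data, and it calls for a stated rule rather than a criticism of how deaths are counted. Neither primary outcome nor the sample size is touched.

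This rests on the forms as printed. The hospital admission form and the manual of operation are not in the text at hand, so the scope of the former is taken from the protocol's description. The point deserves correction before the pooled comparison is reported.

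**What to change.** - In Tables 6 and VI, restate the outcome as postpartum hospital stay of 7 days or more for any reason, computed as item 42 minus item 43. Add a sensitivity analysis that excludes mothers whose newborn was admitted to intensive or special care (56a). The restated outcome fits the Executive Summary, which treats days in hospital as a general measure of maternal morbidity.
- If the maternal qualifier is to be kept, add a coded reason beside item 42. This helps only where forms can still be changed; Khon Kaen follow-up ended in October 1997.
- State, using item 41a, how an in-hospital death before day 7 is handled, so that it is not scored as a short stay.
- Correct the item numbers in Table 6 to the printed form, here to 42-43.
- Amend section 4.9.1 so that item 42 is completed at discharge.

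The restatement uses existing fields and costs only wording. Its drawback is that a stay for any reason is less specific to maternal disease. The alternative costs one extra code on the form.
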